11.4.1 Datasets to be analysed, analysis populations

Analysis of the primary and secondary outcome measures will be only performed with those participants, who completed all tests and investigations. There will be replacement of Drop-Outs until data of 34 participants are completed. Furthermore, subject performance will be analysed regarding

statistical outliers and might be removed from analyses. Drop-outs and statistical outliers will be thoroughly described.

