ISO	International Organisation for Standardisation
ITT	Intention to treat
MADRS-S	Montgomery-Asperg Depression Self-rating Scale
MD	Medical Device
MedDO	Medical Device Ordinance (in German: MepV, in French: ODim)
NA	Not applicable
NG/ML	Nanogram per millilitre
PI	Principal Investigator
SD	Source Data
SDV	Source Data Verification
SOP	Standard Operating Procedure
SPC	Summary of product characteristics
SUSAR	Suspected Unexpected Serious Adverse Reaction
THC	Delta-9-tetrahydrocannabinol
TMF	Trial Master File

STUDY SCHEDULE

Procedure	Visit	Duration (min)	Starting time Visit 1 1 day (+ 3 month) after Tel. Screening	Starting time Visit 2 2 week (+ 8 week) after Visit 1
Telephonescreening				
Inclusion / Exclusion criteria		10	-	-
Screening				
Informed consent	Visit 1	10	00:10	-
MADRS-S		5	00:20	-
Sociodemographic questionnaire		2	00:25	-
Mental - Health questionnaire		5	00:27	-
Concomitant medication		2	00:32	-
Inclusion / Exclusion criteria		1	00:34	-
Test battery 1, 2				
Urine sample	Visit 1, Visit 2 (cross-over)	8	00:35	00:00
AE / Medication Log		1	00:43	00:08
Primary Endpoint: Words learning and immediate recall		2	00:44	00:09
Vape		15	00:46	00:11
Secondary Endpoint: n-back		15	01:01	00:26
VAS of mood, arousal Confounding factors: VAS of motivation, tiredness, headache, tolerance		1	01:16	00:41
Primary Endpoint: Words short delay recall		3	01:17	00:42
Overall time			80min	45min
End Visit 1 and Visit 2				

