There will be a short examination consisting of a THC test, concomitant medication and adverse events. A THC test will be performed in a urine sample according to instructions of THC-Test, MedicTest. The test strip detects THC consumption with a sensitivity of 25 NG/ML. The detection time from last consumption least 3-5 days depending of the consumed amount. (The THC tests will be stored with IMP at the same conditions). Participants eligible for the study will start with the verbal memory task, i.e. learning a list of 15 words (for details see chapter 5.1), followed by an immediate free recall.

Then the participant vapes 0.25mL of the e-Liquid (CBD or perfumed e-Liquid on visit 1 or visit 2 according to the randomization list). After approx. 15 minutes of vaping he/she will perform on the 0-, and 2-back task, followed by some VAS (for details see chapter 5.2). Then, short delay recall of the words will be assessed (for detail see study schedule table).

At the end of each test day participants will be interviewed regarding their actual wellbeing. If there are no complaints / symptoms they can be dismissed. In case of minor health problems, the participant will have to stay in the study centre under medical control until recovery.

The same memory/cognitive test battery will be administered in test days 1 and 2 using parallel versions of the primary and the main secondary outcome measures.

A study compensation of CHF 70 will be paid at the end of visit 2. Screening Failures and Drop-Outs receive a pro rata compensation.

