11.4 Planned Analyses

All analyses will be done in R. Episodic memory performance (memory free recall) and secondary variables of interest will be analyzed by calculating linear mixed models with subject as random effect, experimental condition (Cannabidiol versus placebo) as contrast of interest (fixed effect) as well as the interaction term between experimental condition and covariates (sex, age). In case of significant interactions between covariates and experimental condition, post-hoc tests will be applied to describe the interaction.

Furthermore, to control for possible confounders, possible confounders (words immediate recall, MADRS-S, sociodemographic variables, VAS for mood / arousal / motivation / tiredness / headache / tolerance), subjects' believe about group allocation, will be entered into the model as covariates (each covariate entering the statistical analyses separately).

In case of no significant influence of covariates on dependent variables and in case of no significant interaction of covariate and experimental condition, we will consider to remove covariates out of the statistical model in order to reduce model complexity as far as possible (calculate t-tests in the simplest case).

To illustrate the influence on episodic memory change between experimental conditions, the delta values will be calculated and used dependent variable in an additional analyses. The delta values correspond to the difference in task performance between experimental conditions.

For interim analyses refer to 11.4.3.

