11.4.2 Primary Analysis

Primary outcome analyses will be performed after completed data sampling (see 11.3, 11.4) by study statistician.

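### Outlier removal has no stated rule and no fit is labelled primary, so two-sided 0.05 is not guaranteed for the one primary outcome

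*Combined protocol and SAP*

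**What the plan says.** Section 11 tests a single primary outcome at two-sided 0.05 and waives multiplicity correction because there is only one.

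Section 11.4 names a starting model: a linear mixed model with subject as random effect, "experimental condition (Cannabidiol versus placebo) as contrast of interest (fixed effect"), and interactions of condition with sex and age. The synopsis adds type II sums of squares. Possible confounders then come in, with "each covariate entering the statistical analyses separately": immediate recall, MADRS-S, sociodemographic variables, six VAS ratings and belief about allocation. If neither a covariate nor its interaction with condition is significant, "we will consider to remove covariates out of the statistical model", ending in a t-test in the simplest case. An additional analysis uses delta values: "The delta values correspond to the difference in task performance between experimental conditions".

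Section 11.4.1 restricts the efficacy analyses to completers and allows subjects to be dropped as "statistical outliers and might be removed from analyses". Drop-outs and outliers are to be described. Section 11.4.2 adds only this: "Primary outcome analyses will be performed after completed data sampling (see 11.3, 11.4) by study statistician".

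The Study Schedule places "VAS of mood, arousal Confounding factors: VAS of motivation, tiredness, headache, tolerance" after vaping and the n-back task and just before delayed recall. The section on the cognitive testing visits gives the same order: vaping, n-back, "followed by some VAS (for details see chapter 5.2"), then recall.

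**The concern.** Waiving correction because there is one outcome is sound only if one analysis produces the p-value. Two steps are left open until the outcome data exist.

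- **Outliers.** Removal is optional, and performance could mean a visit score, an overall score or the CBD-minus-placebo difference. These choices have different error rates. Removing the largest differences shrinks the estimated standard deviation, and an ordinary t-test does not allow for that.
- **Model.** After the one-covariate fits and the optional reduction, no fit is labelled primary.

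A related but separate matter is that the VAS ratings follow dosing. Section 3.7 lists somnolence as a CBD risk, so tiredness may itself be a result of treatment. A fit that adjusts for it asks about CBD at equal tiredness, whereas sections 4.2 and 11.1 ask about the effect of CBD on episodic memory.

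**Working it through.** **1. The plan's own figure.** Inputs from section 11.2: paired t-test, dz = 0.5, N = 34, alpha 0.05, power 80%. The noncentrality is 0.5 × √34 = 2.915 and the two-sided critical value on 33 df is 2.035. Exact power is 80.8%, against 79.5% at N = 33. N = 34 is reproduced, as a two-sided test.

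**2. A mechanical outlier rule.** The plan gives no threshold or correlation, so these are assumptions: bivariate normal scores, no CBD effect, 34 subjects, within-subject correlation 0.3, 0.5 or 0.7, and 100,000 simulated trials per setting. Subjects beyond k sample SDs, or outside box-plot fences of 1.5 IQR, are removed. An ordinary paired t-test follows. Simulation error is √(0.10 × 0.90 / 100,000), about 0.1 percentage point, at a rate of 10%.

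| Screened variable | 3 SD | 2.5 SD | 2 SD | Box-plot |
|---|---|---|---|---|
| Difference | 5.3–5.4% | 6.7–6.8% | 10.1–10.3% | about 7.9% |
| Either raw visit score | 5.0–5.2% | 5.4–6.0% | 6.4–8.3% | 5.6–6.6% |
| Overall score (two-visit mean) | about 5% | about 5% | about 5% | 4.9% |

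With no removal the rate is 4.9–5.0%. Screening on the overall score is harmless because, with equal variances, the mean of two normal scores is independent of their difference. Screening on differences removes on average 0.04, 0.30 and 1.4 of 34 subjects at 3, 2.5 and 2 SD. With scores rounded to 0–15 counts (mean 8 or 10, SD 2.5, correlation 0.5), the 2 SD rates are 10.3–10.4% on differences and 7.4–7.9% on raw scores.

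**3. Dropping a covariate by significance.** The recall difference is regressed on one covariate difference, and the intercept is the condition effect. The covariate is unaffected by the drug and has an assumed correlation of 0 to 0.5 with the recall difference. Type I error is 4.9–5.2% if it is always kept. It is 5.1–5.5% if it is kept only when p < 0.05 and a t-test is used otherwise. Main effects of subject-level covariates (MADRS-S, sociodemographics) leave the balanced within-subject contrast essentially unchanged.

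**4. A post-dose VAS.** Let CBD shift the VAS by v, in SDs of its within-subject difference, and let rho be its correlation with the recall difference. Then, in SDs of the recall difference:

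adjusted effect = total effect − rho × v

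With no total effect, v = 0.5 and rho = −0.3, the adjusted effect is 0 − (−0.3 × 0.5) = 0.15. With a zero total effect, the adjusted condition test rejects as follows (v and rho are assumed):

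| rho | v = 0.3 | v = 0.5 | v = 0.8 |
|---|---|---|---|
| −0.1 | 5.3% | 5.8% | 6.4% |
| −0.3 | 7.9% | 12.3% | 19.8% |
| −0.5 | 15.3% | 30.1% | 52.0% |

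These are rejection rates for a different quantity. They are not the type I error of the starting model.

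**5. What keeping every score can cost.** Assume that 3% of visit scores carry extra error with an SD of 4 score SDs, at correlation 0.5. Power at dz = 0.5 is about 60% with no removal and about 73% after removal at 3 SD on raw scores, with type I error of 5.3% for the latter. The 0–15 range of the word count limits how far this can go.

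**The case against.** **The primary model is not wholly open.** This stands in part. Section 11.4 calls condition the contrast of interest in a named model, section 11.4.2 refers back to it, and the one-covariate fits can be read as robustness checks. A reader might infer that there is no primary model at all, but the text does not support that. What is missing is the label, together with a firm rule in place of an option to reduce.

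**Performance need not mean the difference.** This also stands. Section 11.4 keeps delta values for an additional, illustrative analysis. Screening on overall score costs nothing, and 3 SD costs almost nothing on either of the other two variables. The text does not choose among these readings.

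**There are safeguards.** Section 6.2.3 blinds the team, section 11.4.1 promises a description of outliers, and section 12.2.4 records exclusion reasons and applies them when the analysis database is built. These give transparency and a place for exclusions before analysis. None sets an outlier rule or names the primary fit. Blinding does not remove the inflation in the table, which arises under a rule applied mechanically.

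**Trimming can help.** Correct when scores are contaminated, as step 5 shows. A reader might conclude from clean normal data that removal generally loses power. That does not follow, since such data contain no aberrant scores.

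**Conclusion.** The concern holds in limited form. The plan does not fix the rule or the fit behind its one primary p-value, so the 0.05 level is not guaranteed. Across the mechanical outlier rules examined, type I error runs from about 5% to 10.3% under assumed normal scores with N = 34. The upper end needs a 2 SD rule applied to differences. Stating a threshold would not by itself restore 5% if that rule were the one chosen. Significance-based dropping of one drug-unaffected covariate is a minor contributor.

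Two stronger readings are not supported. One is that error reaches 21–26%. That is a simulated worst case in which the smallest p-value over many outlier and covariate options is always reported, and the documents do not say that the team would do this. The other is that the VAS rates, up to 52%, are false-positive rates of the planned analysis. They rest on shifts and correlations with no source in the documents, and they matter only if a VAS-adjusted fit becomes the primary result. The sound conclusion is narrower: such a fit does not estimate the total effect of CBD on recall and should not be primary.

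The change should be made, because it affects the single confirmatory test and is nearly free.

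**What to change.** Amend sections 11.4, 11.4.1 and 11.4.2.

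1. **Population.** The primary analysis includes all completers with delayed recall at both visits, with no removal based on outcome values. Exclusions are only for documented technical failure, decided before unblinding. Report the outlier-excluded result, with variable and threshold stated in advance, as a labelled sensitivity analysis.
2. **Model.** Name one primary mixed model with a fixed set of pre-dose covariates, kept whatever their p-values. One example is condition and immediate recall (measured before vaping) with random subject. State whether the planned condition-by-sex and condition-by-age terms belong to this model or to secondary models. Label all VAS-adjusted, belief-adjusted and reduced fits, including the t-test, as sensitivity analyses.

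The cost is wording only: no added participants, visits or measurements. One pre-dose covariate that is always kept holds type I error at 4.9–5.2% and gives power of 80–89% at dz = 0.5 (assumed correlation 0 to 0.5 with the recall difference), against 81% for the t-test. The downside is that truly aberrant scores stay in the primary result and can lower its power, by the order shown in step 5 of the working if contamination is as heavy as assumed there. The sensitivity analysis would show this.

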11.4.2 Primary Analysis

Primary outcome analyses will be performed after completed data sampling (see 11.3, 11.4) by study statistician.

11.4.3 Secondary Analyses

Secondary outcome analyses will be analysed analogue to primary analyse (see 11.3, 11.4). Subgroup analyses will be performed in case of significant interactions between covariates and experimental condition in order to describe the interaction (see 11.4).

Interim analyses

No interim analyses will be applied.

11.4.4 Safety analysis

Safety analyses will be performed after data sampling completion analogue to the analyses of primary and secondary analyses.

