4.4 Safety Objectives

The study aims to assess tolerability of CBD in terms of incidence of side effects e.g. headache, gastrointestinal side effects etc.

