5.4 Safety Outcomes

Safety outcome variables will consist of rate of adverse events in general.

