11. STATISTICAL METHODS

A within-subject design is performed to achieve more Power than a between-subject design by partitioning between-subject variance out of the error variance. No carryover-effects (e.g. practice, fatigue) are expected.

A significance level of $p < 0.05$ (two-sided) will be considered as significant. As there is only one primary outcome measure, no Bonferroni correction will be applied.

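### Section 11.4.4 sends adverse-event rates to the linear model or t-test of 11.4; if events are few, intervals for incidence come out too narrow and too reassuring

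*Combined protocol and SAP*

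**What the plan says.** Section 4.4 sets the safety objective as "tolerability of CBD in terms of incidence of side effects". Section 5.4 names one safety outcome: "Safety outcome variables will consist of rate of adverse events in general". Section 11.4.4 then gives the analysis in a single sentence: "Safety analyses will be performed after data sampling completion analogue to the analyses of primary and secondary analyses".

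The analyses it points to are in section 11.4. Recall and the secondary variables are analysed by "calculating linear mixed models with subject as random effect", with condition as fixed effect and condition-by-sex and condition-by-age interactions. If covariates fall out, the model may be reduced ("calculate t-tests in the simplest case").

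Two sections bear on who is analysed. Section 7.4 puts everyone who received study medication into the safety analysis. Section 11.4.1 restricts the primary and secondary analyses to completers and allows statistical outliers to be removed.

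**The concern.** Incidence is a proportion: the share of exposed participants with an AE. A linear model with normal errors, or a t-test, suits a recall score but not a proportion near zero in a few dozen people. Its standard error shrinks to nothing as events become rare, and its limits can fall below zero.

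What is at stake is the tolerability statement. Intervals that are too narrow at the top err towards reassurance, which is the wrong direction for safety. If the cross-reference also carries over the analysis set, participants withdrawn because of an AE, a withdrawal reason listed in 7.4, would drop out of the safety estimate.

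**Working it through.** **Inputs.** n = 34 (sections 11.2 and 7.4), the smallest possible safety set because drop-outs are replaced. Level: "A significance level of $p < 0.05$ (two-sided) will be considered as significant" (section 11). Method: section 11.4. The documents give no AE rate, so the event numbers and true rates below are assumptions.

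**The plan's own figure.** For a paired t-test with dz = 0.5 and two-sided 0.05, noncentral-t power is 80.8% with 34 pairs and 79.5% with 33. N = 34 is reproduced. It concerns recall; there is no AE figure to reproduce.

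**Interval for one product's incidence.** With x events and p = x/34, the t-interval is p ± 2.0345 × sqrt(p(1 − p)/33). For x = 1: 0.0294 ± 2.0345 × 0.0294, or −3.0% to 8.9%. The exact (Clopper-Pearson) upper limit for x = 0 is 1 − 0.025^(1/34) = 10.3%.

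| Events of 34 | t-interval (%) | Exact 95% CI (%) |
|---|---|---|
| 0 | 0 to 0 | 0 to 10.3 |
| 1 | −3.0 to 8.9 | 0.1 to 15.3 |
| 2 | −2.5 to 14.2 | 0.7 to 19.7 |
| 3 | −1.2 to 18.9 | 1.9 to 23.7 |
| 4 | 0.4 to 23.2 | 3.3 to 27.5 |

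**How often the t upper limit falls below the true rate (nominal 2.5%).**

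- True rate 3%: whenever x = 0, so 0.97^34 = 35.5%.
- True rate 5%: whenever x = 0, so 0.95^34 = 17.5%.
- True rate 10%: whenever x ≤ 1, so 0.9^34 + 34 × 0.1 × 0.9^33 = 2.8% + 10.5% = 13.3%.
- True rate 20%: whenever x ≤ 3, which is 7.0%.

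Coverage of the nominal 95% t-interval at these four rates is 64%, 82%, 86% and 92%.

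**Mixed model.** Take 4 participants with an AE only after CBD and none with one after placebo (4–0). The random-intercept variance is estimated at zero and both products share one pooled variance. The sample variances are 0.107 (CBD) and 0 (placebo), with mean 0.0535, so SE = sqrt(0.0535/34) = 0.0397. Placebo is then 0% ± 1.96 × 3.97%, or −7.8% to 7.8%, against an exact upper limit of 10.3%. CBD is 4.0% to 19.5%, against an exact upper limit of 27.5%.

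**Comparison of products.** For 4–0 the paired t is 0.1176/0.0561 = 2.098 on 33 df. Exact McNemar is 2 × (1/2)^4 = 0.125; mid-p is half of that here.

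| Discordant split | Paired t | Asymptotic McNemar | Mid-p | Exact |
|---|---|---|---|---|
| 4–0 | 0.044 | 0.0455 | 0.0625 | 0.125 |
| 5–0 | 0.023 | 0.025 | 0.031 | 0.0625 |
| 7–1 | 0.032 | 0.034 | 0.039 | 0.070 |

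The mixed-model Wald p for 4–0 is 0.036.

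Under equal AE rates of 3, 5, 10, 15, 20 and 30%, with independence within participant, the paired t-test rejects in 1.3, 3.4, 4.8, 4.3, 4.3 and 4.6% of trials. Exact McNemar rejects in 0.04, 0.3, 1.3, 2.0, 2.3 and 2.7%.

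**Analysis set.** 7.4 and 11.4.1 name different populations, and 11.4.4 does not say which one its cross-reference carries over.

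**The case against.** **The reading is inferred.** Section 11.4.4 could be taken as a statement about timing, and 11.4 names recall and secondary variables, not AEs. But timing already has its own phrase in that sentence, and 11.4.3 uses the same word for method. If it were timing only, the plan would have no safety method at all and the same repair would be needed.

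**Sparse yes/no data is assumed.** This stands. The documents give no rate, and a rate could mean counts. Low incidence is plausible for a single low-dose use that section 2.2 describes as minimal risk, but it is not stated. A normal-error model would suit small counts poorly too.

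**No per-product interval is requested.** Also true: 11.4 plans a condition contrast. The intervals above show what the named method yields if incidence, the objective in 4.4, is estimated with it.

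**Stronger readings that the evidence does not support.** A reader might infer that the plan will report negative AE rates. Condition means cannot be negative; what goes negative is mainly the lower confidence limit at 1 to 3 events. Negative fitted values arose in simulations of the model with sex and age interactions (82% of trials at assumed rates of 10% vs 5%, 43% at 30% vs 15%). A reader might also infer that the t-test produces false positives. Its type I error stayed below 5% in every case computed and its p-values track asymptotic McNemar. Mid-p agrees that 5–0 and 7–1 are significant, so much of the gap is the conservatism of the exact test. The zero random-effect variance likewise belongs to the example: one participant with an AE under both products, added to 4–0, makes the within-subject covariance positive.

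**McNemar alone has a gap.** It drops participants exposed only once, including those withdrawn for AEs. This stands, and the repair must deal with it.

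**Conclusion.** The concern holds in limited form. On its most natural reading, 11.4.4 applies a method that does not suit an incidence objective, and nothing suitable is named elsewhere. Provided AEs are few, the t-interval's upper limit at n = 34 is too low by 10.3 percentage points with no events (10.3 − 0) and by 6.4, 5.5 and 4.8 points with 1, 2 and 3 events (15.3 − 8.9, 19.7 − 14.2, 23.7 − 18.9). In the 4–0 mixed-model example the placebo shortfall is 2.5 points (10.3 − 7.8). The p-value point is secondary: a single dataset such as 4–0 can cross 0.05 by t-test and not by mid-p or exact McNemar, but error rates are not inflated.

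The unclear analysis set is a separate reason to rewrite the sentence. Sample size and the primary analysis are untouched, but tolerability is a stated objective and deserves a stated method.

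**What to change.** Replace section 11.4.4 with:

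> Safety is analysed in everyone who received at least one study product (section 7.4), without outlier removal. For each product, the number and percentage of exposed participants with at least one AE is given with an exact (Clopper-Pearson) 95% CI. Products are compared in participants exposed to both, by exact or mid-p McNemar test (one to be named before unblinding), with the paired risk difference. AEs in participants exposed once are included in the per-product rates and listed. AEs with onset between visits are assigned to the product last used.

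The cost is one short paragraph and trivial programming. Intervals become wider and the comparison more conservative, more so with exact than with mid-p McNemar. The assignment rule gives the visit 1 product an observation window of 14 to 56 days and the visit 2 product only the remainder of that visit. Block randomisation of order (6.2.1) balances this between CBD and placebo, but the report should state it.
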